14.7 Safety: Laboratory

Table 14.3.2.1: Laboratory data: Descriptive statistics of the actual values per time point

Descriptive statistics per lab test category (hematology, biochemistry and coagulation), lab test and unit and time point. Table sorted first by treatment group, then by time point. Each lab test will begin on a new page.

Population: safety population.

Table 14.3.2.2: Laboratory data: Descriptive statistics of the absolute changes from baseline per time point

Descriptive statistics per lab test category (hematology, biochemistry and coagulation), lab test and unit and time point. Table sorted first by treatment group, then by time point. Each lab test will begin on a new page.

Population: safety population.

Table 14.3.2.3: Laboratory data: Descriptive statistics of the percentage changes from baseline per time point

Descriptive statistics per lab test category (hematology, biochemistry and coagulation), lab test and unit and time point. Table sorted first by treatment group, then by time point. Each lab test will begin on a new page.

Population: safety population.

Table 14.3.2.4: Laboratory data: Cross-tabulation of the abnormalities per time point

Cross-tabulation per lab test category (hematology, biochemistry and coagulation), lab test and time point. Table sorted first by treatment group, then by time point. Each lab test will begin on a new page. The table will present the shift in abnormality (L/N/H) at each post-baseline time point versus the baseline abnormality (L/N/H). Tests without normal ranges will not be presented in this table.

Population: safety population.

Table 14.3.2.5: Laboratory data: Additional cross-tabulation of the abnormalities per time point for key parameters

Cross-tabulation per lab test and time point. Table sorted first by treatment group, then by time point. Each lab test will begin on a new page. The table will present the shift in abnormality at each post-baseline time point versus the baseline abnormality, according to the additional categorization described in Section 7.2.5.

ALT, AST, hemoglobin, leukocytes and serum creatinine will be presented in this table.
 Population: safety population.

Table 14.3.2.6: Laboratory data: Cross-tabulation of the worst-case abnormalities

Cross-tabulation per lab test category (hematology, biochemistry and coagulation) and lab test. Each lab test will begin on a new page. The table will present the shift in abnormality (L/N/H/L+H) at the worst post-baseline time point versus the baseline abnormality (L/N/H). Tests without normal ranges will not be presented in this table.
 Population: safety population.

Table 14.3.2.7: Laboratory data: Additional cross-tabulation of the worst-case abnormalities for key parameters

Cross-tabulation per lab test. The table will present the shift in abnormality at the worst post-baseline time point versus the baseline abnormality, according to the additional categorization described in Section 7.2.5.

ALT, AST, hemoglobin, leukocytes and serum creatinine will be presented in this table.
 Population: safety population.

14.8 Safety: ECG

Table 14.3.3.1: ECG: Cross-tabulation of the investigator's conclusion per time point

Cross-tabulation per time point. Table sorted first by treatment group, then by time point. The table will present the shift in conclusion (normal/abnormal NCS/abnormal CS) at each post-baseline time point versus the baseline conclusion (normal/abnormal NCS/abnormal CS).
 Population: safety population.

14.9 Safety: Vital Signs

Table 14.3.4.1: Vital signs: Descriptive statistics of the actual values per time point

Descriptive statistics per test and unit and time point. Table sorted first by treatment group, then by time point. Each test will begin on a new page.
 Population: safety population.

Table 14.3.4.2: Vital signs: Descriptive statistics of the changes from baseline per time point

Descriptive statistics per test and unit and time point. Table sorted first by treatment group, then by time point. Each test will begin on a new page.
 Population: safety population.

14.10 Immunogenicity

Table 14.3.5.1: Immunogenicity: ADA incidence based on ADA assay results

The table will present the number and percentage of subjects per ADA subject category by treatment group and by analysis period. Subject categories, treatment groups and analysis periods are given in Section 9.1.1.1.

Population: safety population.

Table 14.3.5.2: Immunogenicity: Incidence of drug-induced TE ADA status and pre-Ab status based on mADA assay results

The table will present a summary by treatment group and analysis period of (1) the number and percentage of subjects within each mADA subject category, (2) the number and percentage of subjects classified as TE ADA within the pre-Ab negative and within the pre-Ab positive population, and (3) the number and percentage of subjects classified as pre-Ab negative, pre-Ab positive, drug-induced TE negative and drug-induced TE positive. Subject categories, treatment groups and analysis periods are given in Section 9.1.1.2.

Population: subset of safety population consisting of subjects who were classified as ADA positive based on ADA data.

Population: safety population.

Table 14.3.5.3: Immunogenicity: Incidence of drug-induced TE ADA status and pre-Ab status based on ADA/mADA assay results (overall subject classification)

The table will present a summary by treatment group and analysis period of (1) the number and percentage of subjects within each overall subject category, (2) the number and percentage of subjects classified as TE ADA within the pre-Ab negative and within the pre-Ab positive population, and (3) the number and percentage of subjects classified as pre-Ab negative, pre-Ab positive, drug-induced TE negative and drug-induced TE positive. Subject categories, treatment groups and analysis periods are given in Section 9.1.1.2.

Population: safety population.

Table 14.3.5.4: Immunogenicity: Incidence of pre-dose NAb status and TE NAb status based on NAb assay result

The table will present a summary by treatment group and analysis period of (1) the number and percentage of subjects within each NAb subject category, and (2) the number and percentage of subjects classified as pre-dose negative, pre-dose positive, TE negative and TE positive. Subject categories, treatment groups and analysis periods are given in Section 9.1.2.

Population: safety population.

Table 14.3.5.5: Immunogenicity: Incidence of pre-dose NAb status and TE NAb status based on alternative NAb (null variant) assay result

The table will present a summary by treatment group and analysis period of (1) the number and percentage of subjects within each alternative NAb subject category, and (2) the number and percentage of subjects classified as pre-dose negative, pre-dose positive, TE negative and TE positive. Subject categories, treatment groups and analysis periods are given in Section 9.1.3.

Population: safety population.

Table 14.3.5.6: Immunogenicity: Incidence of drug-induced TE ADA status and pre-Ab status based on ADA and mADA assay results (overall subject classification) by hypersensitivity reaction

Table 14.3.5.3, repeated for each category of hypersensitivity reaction.

CONFIDENTIAL

Population: safety population.

Table 14.3.5.7: Immunogenicity: Incidence of drug-induced TE ADA status and pre-Ab status based on ADA and mADA assay results (overall subject classification) by treatment extension (Y/ N)

Table 14.3.5.3, repeated for each category of hypersensitivity reaction.

Population: safety population.

Table 14.3.5.8: Immunogenicity: Incidence of drug-induced TE ADA status and pre-Ab status based on ADA and mADA assay results (overall subject classification) by Rituximab use

Table 14.3.5.3, repeated for each category of hypersensitivity reaction.

Population: safety population.

Table 14.3.5.9: Immunogenicity: drug concentration by overall subject category (based on ADA/mADA assay results)

Descriptive statistics of drug concentrations by visit and by overall subject category for (1) Caplacizumab during DB period, (2) OL Caplacizumab (after Caplacizumab) during OL Caplacizumab period, and (3) OL Caplacizumab (after Placebo) during OL Caplacizumab period. Subject categories, treatment groups and analysis periods are given in Section 9.1.1.2.

Population: safety population

Table 14.3.5.10: Immunogenicity: RICO activity by overall subject category (based on ADA/mADA assay results)

Descriptive statistics of RICO activity by visit and by overall subject category for (1) Caplacizumab during DB period, (2) Placebo during DB period, (3) OL Caplacizumab (after Caplacizumab) during OL Caplacizumab period, and (4) OL Caplacizumab (after Placebo) during OL Caplacizumab period. Subject categories, treatment groups and analysis periods are given in Section 9.1.1.2.

Population: safety population

Table 14.3.5.11: Immunogenicity: Percent change from baseline in vWF:Ag concentration by overall subject category (based on ADA/mADA assay results)

Descriptive statistics of percent change from baseline of vWF:Ag concentrations by visit and by overall subject category for (1) Caplacizumab during DB period, (2) Placebo during DB period, (3) OL Caplacizumab (after Caplacizumab) during OL Caplacizumab period, and (4) OL Caplacizumab (after Placebo) during OL Caplacizumab period. Subject categories, treatment groups and analysis periods are given in Section 9.1.1.2.

Population: safety population

Table 14.3.5.12: Immunogenicity: Time to platelet count response by overall subject category (based on ADA/mADA assay results)

Descriptive statistics of time to platelet count response, based on KM analysis, by overall subject category for (1) Caplacizumab during DB period, (2) Placebo during DB period, (3) OL Caplacizumab (after Caplacizumab) during OL Caplacizumab period, and (4) OL

Caplacizumab (after Placebo) during OL Caplacizumab period. Subject categories, treatment groups and analysis periods are given in Section 9.1.1.2.

Population: safety population

Table 14.3.5.13: Immunogenicity: drug concentration by NAb assay subject category

Descriptive statistics of drug concentrations by visit and by NAb subject category for (1) Caplacizumab (no OL Caplacizumab) during DB period, (2) OL Caplacizumab (after Caplacizumab) during overall study period, and (3) OL Caplacizumab (after Placebo) during OL Caplacizumab period. Subject categories, treatment groups and analysis periods are given in Section 9.1.2.

Population: safety population

Table 14.3.5.14: Immunogenicity: RICO activity by NAb assay subject category

Descriptive statistics of RICO activity by visit and by NAb subject category for (1) Caplacizumab (no OL Caplacizumab) during DB period, (2) Placebo (no OL Caplacizumab) during DB period, (3) OL Caplacizumab (after Caplacizumab) during overall study period, and (4) OL Caplacizumab (after Placebo) during OL Caplacizumab period. Subject categories, treatment groups and analysis periods are given in Section 9.1.2.

Population: safety population

Table 14.3.5.15: Immunogenicity: Percent change from baseline in vWF:Ag concentration by NAb assay subject category

Descriptive statistics of percent change from baseline of vWF:Ag concentrations by visit and by NAb subject category for (1) Caplacizumab (no OL Caplacizumab) during DB period, (2) Placebo (no OL Caplacizumab) during DB period, (3) OL Caplacizumab (after Caplacizumab) during overall study period, and (4) OL Caplacizumab (after Placebo) during OL Caplacizumab period. Subject categories, treatment groups and analysis periods are given in Section 9.1.2.

Population: safety population

Table 14.3.5.16: Immunogenicity: Time to platelet count response by NAb assay subject category

Descriptive statistics of time to platelet count response, based on KM analysis, by NAb subject category for (1) Caplacizumab during DB period, (2) Placebo during DB period, (3) OL Caplacizumab (after Caplacizumab) during OL Caplacizumab period, and (4) OL Caplacizumab (after Placebo) during OL Caplacizumab period. Subject categories, treatment groups and analysis periods are given in Section 9.1.2.

Population: safety population

Table 14.3.5.17: Immunogenicity: drug concentration by alternative NAb assay subject category

Descriptive statistics of drug concentrations by visit and by alternative NAb subject category for (1) Caplacizumab during DB period, (2) OL Caplacizumab (after Caplacizumab) during overall study period, and (3) OL Caplacizumab (after Placebo) during OL Caplacizumab period. Subject categories, treatment groups and analysis periods are given in Section 9.1.3.

Population: safety population

Table 14.3.5.18: Immunogenicity: RICO activity by alternative NAb assay subject category

CONFIDENTIAL

Descriptive statistics of RICO activity by visit and by alternative NAb subject category for (1) Caplacizumab during DB period, (2) Placebo during DB period, (3) OL Caplacizumab (after Caplacizumab) during overall study period, and (4) OL Caplacizumab (after Placebo) during OL Caplacizumab period. Subject categories, treatment groups and analysis periods are given in Section 9.1.3.

Population: safety population

Table 14.3.5.19: Immunogenicity: Percent change from baseline in vWF:Ag concentration by alternative NAb assay subject category

Descriptive statistics of percent change from baseline of vWF:Ag concentrations by visit and by alternative NAb subject category for (1) Caplacizumab during DB period, (2) Placebo during DB period, (3) OL Caplacizumab (after Caplacizumab) during overall study period, and (4) OL Caplacizumab (after Placebo) during OL Caplacizumab period. Subject categories, treatment groups and analysis periods are given in Section 9.1.3.

Population: safety population

Table 14.3.5.20: Immunogenicity: Time to platelet count response by alternative NAb subject category

Descriptive statistics of time to platelet count response, based on KM analysis, by alternative NAb subject category for (1) Caplacizumab during DB period, (2) Placebo during DB period, (3) OL Caplacizumab (after Caplacizumab) during overall study period, and (4) OL Caplacizumab (after Placebo) during OL Caplacizumab period. Subject categories, treatment groups and analysis periods are given in Section 9.1.3.

Population: safety population

Table 14.3.5.21: Immunogenicity: ADA/mADA log10(titer) over time

Descriptive statistics of ADA/mADA log10(titer) by visit and by treatment group (Caplacizumab during DB period, Placebo during DB period, OL Caplacizumab [after Caplacizumab] during OL Caplacizumab period, and OL Caplacizumab [after Placebo] during OL Caplacizumab period).

Population: safety population

Table 14.3.5.22: Immunogenicity: NAb log10(titer) over time

Descriptive statistics of NAb log10(titer) by visit and by treatment group (Caplacizumab [no OL Caplacizumab] during DB period, Placebo [no OL Caplacizumab] during DB period, OL Caplacizumab [after Caplacizumab] during overall study period, and OL Caplacizumab [after Placebo] during OL Caplacizumab period).

Population: safety population

Table 14.3.5.23: Immunogenicity: Alternative NAb log10(titer) over time

Descriptive statistics of alternative NAb log10(titer) by visit and by treatment group (Caplacizumab during DB period, Placebo during DB period, OL Caplacizumab [after Caplacizumab] during overall study period, and OL Caplacizumab [after Placebo] during OL Caplacizumab period).

Population: safety population

Table 14.3.5.24: Immunogenicity: ADA/mADA incidence over time

Incidence of positive ADA or mADA samples by visit and by treatment group (Caplacizumab during DB period, Placebo during DB period, OL Caplacizumab [after Caplacizumab] during OL Caplacizumab period, and OL Caplacizumab [after Placebo] during OL Caplacizumab period).

Population: safety population

Table 14.3.5.25: Immunogenicity: NAb incidence over time

Incidence of positive NAb samples by visit and by treatment group (Caplacizumab [no OL Caplacizumab] during DB period, Placebo [no OL Caplacizumab] during DB period, OL Caplacizumab [after Caplacizumab] during overall study period, and OL Caplacizumab [after Placebo] during OL Caplacizumab period).

Population: safety population

Table 14.3.5.26: Immunogenicity: Alternative NAb incidence over time

Incidence of positive alternative NAb samples by visit and by treatment group (Caplacizumab during DB period, Placebo during DB period, OL Caplacizumab [after Caplacizumab] during overall study period, and OL Caplacizumab [after Placebo] during OL Caplacizumab period).

Population: safety population

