- Daily subcutaneous (s.c.) dose: within 2 hours of completing each daily PE, a s.c. injection of 10 mg study drug will be administered daily throughout the full duration of PE treatment.

[†] Of note, the PE administered prior to randomization (PE of unrestricted intensity) may be given prior to signing ICF (as part of standard of care) and may be spread over 2 or more sessions in 24 hours as long as considered part of the 1 intense PE for the treatment of the presenting TTP episode. Note that the maximum time allowed between the start of first PE (i.e., PE administered prior to randomization) and the start of the first PE after randomization (i.e., the first on-study PE) is 24 hours.

[‡] For logistical reasons, the Sponsor needs to be contacted if the daily PE period exceeds beyond 30 days.

It is expected that subjects are hospitalized for the duration of the daily PE period. Exceptions should be discussed with the Medical Monitor.

30-day post-daily PE period

Daily s.c. administration of 10 mg study drug will continue for a period of 30 days after stop of daily PE. No adjustment to this period will be made for tapering of PE. After discharge from hospital, subjects are allowed to self-administer (after learning how to prepare and s.c. inject the study drug).

Treatment extension period

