This also highlights the challenges of conducting a clinical trial in a very rare condition which is further complicated by the emergency care setting and the urgency of initiating appropriate treatment. Previous randomized trials in TTP were terminated prematurely due to low recruitment rates, including the TITAN trial which was terminated early for this after enrolling 75 subjects out of a planned 110, at 32 of 56 approved sites in 13 countries worldwide over a period of 3 years. The STAR study enrolled 3 patients of the planned 220 from April 2009 to February 2010 after which it was terminated due to low recruitment at

the 17 participating sites [30]; and the ARC1779 trial which enrolled 9 subjects of the planned 100 subjects.

Dose Selection Rationale

The pharmacology of caplacizumab is two-fold. Caplacizumab affects the functionality of vWF, leading to inability of vWF to bind to platelets. It also affects the disposition of vWF, leading to transient reductions of total vWF:Ag levels during treatment.

A population PK/PD model was developed using total vWF:Ag levels as PD endpoint on data pooled from the different clinical trials performed in healthy volunteers and in patients. This model adequately describes the PK and PD observations in the TITAN trial. *In vitro* experiments identified a correlation between target inhibition and target occupancy, which is similar across a wide range of vWF:Ag levels. These *in vitro* results support that a population PK/PD approach which assesses the effect of caplacizumab on free and total levels of vWF is suited to define adequate dose levels in acquired TTP patients.

The dose of 10 mg used in the TITAN trial was proposed based on the information available on the suppression of vWF by s.c. administration of caplacizumab in healthy volunteers as measured *ex vivo* (ALX-0681-1.1/08).

The efficacy and safety results from the TITAN trial confirm the appropriateness of the 10 mg dose. The 10 mg i.v. loading dose in the TITAN trial ensured caplacizumab exposure was detectable already 5-10 minutes after administration allowing a rapid attainment of the desired drug concentration, while the 10 mg s.c. daily dose assures sufficient daily exposure to maintain the pharmacological effect. The effect on target neutralization was measured through the RICO assay and this demonstrated the desired sustained suppression of RICO activity to < 20% throughout the treatment period.

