4.3 Key Definitions and Labels

4.3.1 Definition of baseline

Baseline is defined as the last non-missing assessment before first administration of study drug.

For assessments with multiple parameters per subject (such as laboratory assessments), baseline will be determined per parameter individually. It is recognized that baseline assessments may thus come from more than one assessment and not just from the “baseline visit” assessment. Baseline will be calculated for each treatment period separately (double-blind treatment and open-label treatment). The assessment on Day 1 of the open-label treatment period, taken before first administration of open-label caplacizumab, will be taken as baseline value for the open-label part.

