4.3.2 Change from baseline and percentage change from baseline

The change from baseline will be calculated for all post-baseline time points as:

Change from baseline at time point t = value at time point t – baseline value.

Percentage change from baseline at time point t = $100 * ((\text{value at time point t} - \text{baseline value}) / \text{baseline value})$.

Change from baseline and percentage change from baseline will be calculated separately for each of the treatment periods from their respective baseline values.

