Subjects with no positive ADA sample will be classified as pre-dose negative, TE negative in the alternative NAb assay. In listings, samples not evaluated in the alternative NAb assay will be indicated as not analyzed (NA). In graphical presentations they will be presented as negative results at the specific sample time points.

Given the possible switch to open-label caplacizumab in case of TTP recurrence, subjects will be classified based on the ADA samples available during the DB period, and the OL period separately. For the latter subject classification, the Day 1 visit of the OL treatment period will be used as baseline visit. Patients who switch to open-label caplacizumab after having received double-blind caplacizumab treatment will be classified based on the DB period and

the overall study period, but not on the OL Caplacizumab period, as the OL Day 1 baseline visit cannot be considered a proper baseline visit for this analysis. Table 7 below provides an overview of the treatment groups for which the incidence in the different classes of the subject classification based on alternative NAb will be calculated, and the analysis periods for which this will be done.

Table 7: Overview of the treatment groups based on alternative NAb

Treatment group	DB period*	OL Caplacizumab period*	Overall study period
Placebo (no OL Caplacizumab)	X		
Caplacizumab (no OL Caplacizumab)	X (i)		
OL Caplacizumab (after Placebo)	X	X (i)	
OL Caplacizumab (after Caplacizumab)	X	Not done	X (i)
Placebo	Combination of 'Placebo (no OL Caplacizumab)' and 'OL Caplacizumab (after Placebo)'		
Caplacizumab	Combination of 'Caplacizumab (no OL Caplacizumab)' and 'OL Caplacizumab (after Caplacizumab)'		
Caplacizumab Total	Combination of 'Caplacizumab (no OL Caplacizumab)' (DB period), 'OL Caplacizumab (after Placebo)' (OL Caplacizumab period), and 'OL Caplacizumab (after Caplacizumab)' (Overall study period), as indicated by (i)		

* FU samples are included in the DB period if the patients are not switching to OL caplacizumab; in the latter case the FU sample is considered part of the OL Caplacizumab period.

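### In SAP Table 14.3.5.11, vWF:Ag percent change for subjects re-treated after double-blind caplacizumab starts from a normally on-drug sample, which hides suppression already present and puts the group on a different scale

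*SAP*

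**What the plan says.** SAP 4.3.1 defines a separate baseline for each treatment period. For the open-label part: "The assessment on Day 1 of the open-label treatment period, taken before first administration of open-label caplacizumab, will be taken as baseline value". SAP 4.3.2 carries this into the derived variable: "Change from baseline and percentage change from baseline will be calculated separately for each of the treatment periods from their respective baseline values".

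SAP 14.10, Table 14.3.5.11, then presents "Descriptive statistics of percent change from baseline of vWF:Ag concentrations by visit and by overall subject category". One of its four groups is "3) OL Caplacizumab (after Caplacizumab) during OL Caplacizumab period", and no other baseline is named. Figure 14.4.1.3 (mean plot) and Figure 14.4.1.4 (scatter plot) use the same groups and the same variable.

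On drug status at the switch, the Protocol Synopsis says: "Daily s.c. administration of 10 mg study drug will continue for a period of 30 days after stop of daily PE". An exacerbation is by definition a recurrence inside that 30-day window. The only relapse that leads to open-label treatment is one that occurs during the treatment extension, while study drug is still being given. On the drug's effect, Protocol 3.1.2 describes caplacizumab as "leading to transient reductions of total vWF:Ag levels during treatment".

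**The concern.** SAP 9.2 plans to relate immunogenicity to the pharmacodynamic markers. Table 14.3.5.11 serves that purpose by asking whether vWF:Ag responds differently in subjects with drug-induced antibodies.

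In the group treated with caplacizumab in both periods, the reference value already contains the drug effect. An intact response then looks like no response. If antibodies had weakened the effect before the switch, the antibody-positive and antibody-negative rows would both sit near zero. The neighbouring groups carry the same column heading but start from a caplacizumab-free value, so a reader who compares panels would be comparing different quantities.

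**Working it through.** The plan states no figure for this point, so there is nothing to reproduce. The check follows the rules through and then applies the SAP formula under each baseline.

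**1. Which baseline applies.** SAP 4.3.1 and 4.3.2 give OL Day 1 for the OL period. The Table 14.3.5.11 groups compare as follows:

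| Group | Baseline | Caplacizumab before it? |
|---|---|---|
| (1) Caplacizumab, DB | DB Day 1, pre-dose | No |
| (2) Placebo, DB | DB Day 1, pre-dose | No |
| (3) OL after caplacizumab | OL Day 1 | Yes, normally daily up to the switch |
| (4) OL after placebo | OL Day 1 | No |

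**2. Is drug still present at OL Day 1?** No washout is planned. Protocol 1.2.4 gives a half-life of 10 to 30 hours for target-bound drug. The fraction of one dose's bound drug left after 24 hours is 2^(-24/t½):
- t½ = 10 h: 0.19
- t½ = 30 h: 0.57

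This ignores accumulation from daily dosing. Protocol 3.4.11 places samples in the daily PE period before that day's PE and before s.c. dosing, so later values in that period are also troughs. Trough is then compared with trough.

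**3. Effect on the reported number.** SAP 4.3.2: percent change = 100 × (value − baseline) / baseline. Set the off-drug level to 1 and let d be the on-drug fall. The documents do not give d, so 20% to 50% is an assumption. Let s be the share of the suppression already present at OL Day 1. The OL-baseline reading is 100 × [(1−d) − (1−sd)] / (1−sd).

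| s | d = 20% | d = 50% |
|---|---|---|
| 0 (same as DB baseline) | −20% | −50% |
| 0.5 | −11.1% | −33.3% |
| 0.8 | −4.8% | −16.7% |
| 1 | 0% | 0% |

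**4. Effect on the antibody comparison.** Assume a 40% fall without antibodies and a 10% fall with them.

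| Subject | From DB baseline | From OL Day 1 |
|---|---|---|
| No antibodies | −40% | (0.6−0.6)/0.6 = 0% |
| Antibodies since DB period | −10% | (0.9−0.9)/0.9 = 0% |
| Antibodies first in OL period | −10% | (0.9−0.6)/0.6 = +50% |

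A contrast already present at the switch disappears. A loss that emerges after the switch shows, but as a rise from the on-drug level and not as a smaller fall.

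**5. How many subjects.** With 132 randomized 1:1 there are 66 per arm. Protocol 1.2.4 reports 3 exacerbations on treatment with caplacizumab in Phase II (8%; the denominator is 36, from 10 subjects = 27.8%). Expected switchers after caplacizumab: 66 × 3/36 = 5.5, or 6.6 at a rate of 10%. Protocol 1.2.5 reports drug-induced treatment-emergent antibodies in 9%: 5.5 × 0.09 = 0.5 and 6.6 × 0.09 = 0.6 subjects. The binomial chance of two or more antibody-positive subjects is 7% with n = 5 and 13% with n = 7.

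**The case against.** The strongest reply is that little depends on this output and that most of the information appears elsewhere.

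- No inferential statistics are derived for immunogenicity (SAP 9.2). The antibody-positive cell will probably hold no one or one person, and with n = 1 SAP 4.2.1 prints only the count and the value. No baseline makes that cell informative as a comparison. This stands.
- RICO activity and drug concentration are summarised as actual values by the same antibody category (Tables 14.3.5.9 and 14.3.5.10). Figure 14.4.1.22 plots vWF:Ag, RICO, PK and titers over time for each ADA-positive subject. The switchers' fall during the DB period is included in group (1), though pooled with non-switchers. These cover the question in part.
- The OL Day 1 rule may be deliberate. SAP 9.1.1.2 also uses OL Day 1 as the baseline visit for the OL antibody classification. That is a rule for classifying antibodies. It does not make an on-drug value a sound reference for a marker that the drug lowers.
- A DB baseline has its own defect. DB Day 1 follows one PE, whereas OL Day 1 precedes the new episode's PE, so the change would run across two episodes and two PE states. This is true and belongs in a footnote.

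A reader might also infer three stronger points, which the documents do not support. First, that the comparison can never show a loss of effect: step 4 shows that a loss emerging in the OL period is visible. Second, that every vWF:Ag table has the fault: Tables 14.3.5.15 and 14.3.5.19 report these subjects over the overall study period, and their only gap is that no baseline is named. Third, that the SAP has itself rejected this baseline for vWF:Ag. The sentence in SAP 9.1.3, "as the OL Day 1 baseline visit cannot be considered a proper baseline visit for this analysis", concerns the alternative NAb classification of the same subjects and supports the point only by analogy.

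**Conclusion.** The point holds for one group in one descriptive table and two figures. Under the SAP's own rules, vWF:Ag percent change for subjects re-treated after DB caplacizumab normally starts from an on-drug value. Suppression, or its loss, already present at OL Day 1 is removed, and the numbers cannot be read against the other three groups.

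The size rests on an assumed fall. At 20% to 50%, intact suppression reads 0% if it was fully present at OL Day 1, and −4.8% to −16.7% if four fifths of it was present. The distortion is smaller where DB doses were missed or interrupted before the switch. The subject count assumes that Phase II rates carry over.

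Importance is low: about 5 to 6 subjects are affected, and the primary and key secondary analyses are untouched. It is still worth correcting, because in so small a group a column that shows full suppression as no change is easily misread.

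**What to change.** In Table 14.3.5.11 and Figures 14.4.1.3 and 14.4.1.4, for OL Caplacizumab (after Caplacizumab) only, compute vWF:Ag percent change from the DB pre-caplacizumab baseline, and show the actual vWF:Ag values alongside. Name the same baseline for this group in Tables 14.3.5.15 and 14.3.5.19, where SAP 4.3.2 could otherwise be applied to the open-label visits.

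Add a footnote that DB Day 1 was drawn after one PE, whereas OL Day 1 precedes the PE for the new episode.

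Write this as an exception attached to these outputs, not as a general edit of SAP 4.3.1 and 4.3.2. OL Day 1 should remain the baseline after placebo and for other parameters; SAP 6.2.2, for example, expressly uses it for OL change in SMMSE.

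The cost is a few lines of table and figure specification and one baseline flag. The sample needed is already scheduled: Protocol Table 2 has a Day 1 pharmacodynamic sample, and Protocol 3.4.11 places it before the i.v. dose.
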